3.3. Study Endpoints

3.3.1. Safety Endpoints

The safety endpoints as measured throughout the long-term dosing of weekly TransCon hGH treatment include the following:

- Incidence of AEs
- Incidence of antibodies against hGH, including neutralizing antibodies
- Incidence of antibodies against PEG
- Incidence of IGF-1 SDS > 2.0, > 3.0 with confirmation
- Parameters of HbA1c and lipids
- Hormone levels, including thyroid status and morning cortisol
- All other hematology and chemistry parameters
- Vital sign measurements

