Synopsis – Trial Design – Dose Adjustment Parameters; 9.6.1 Dose Adjustment Parameters; 9.6.2 Stopping/Dose Reductions; 9.6.2 Stopping/Dose Reductions	Repeat IGF-1 testing no longer required when visit IGF-1 SDS is < 0 or > 2.0 and clinically significant	To align more closely with real-world practice where dose titrations may be recommended after a single (rather than duplicate) IGF-1 test. In the trial to date, the repeat (unscheduled) IGF-1 SDS test results have generally not provided additional meaningful information beyond the initial IGF-1 test done routinely with the scheduled study visits. Furthermore, for some subjects the repeat IGF-1 blood test have represented a time burden associated with minimal benefit. Investigators will continue to have the option to repeat IGF-1 tests at any time during the trial.
Synopsis – Trial Design – Dose Adjustment Parameters	For subjects previously dose-titrated, added provision to allow the maintenance of the current TransCon hGH dose until IGF-1 SDS result is available	To align more closely with real-world practice.
Global	Clarify that DCCs may be (rather than will be) supplied in the United States	Some children in the US may still use vials if they are in a weight bracket not yet served by a current DCC

Section(s)	Change	Rationale
Synopsis - Treatment regimens	Added the word “approximately” in front of 0.24 mg hGH/kg/week	This is the nominal dose; and children are in a bracket
Synopsis - Treatment regimens	Specified that weight-based dose volume or DCC adjustments will follow Table 1 and Table 2 , respectively	Table 2 will be used for subjects using the GH Auto-Injector and accompanying DCCs
Planned number of subjects; Trial population; 8. Subject Population	Changed from 400 to 300	To clarify the known projected enrollment
Synopsis – Criteria for Evaluation	Deleted ‘with confirmation’ from Safety Endpoints on Incidence of IGF-1 SDS>2.0, 3.0	The requirement for a repeat IGF-1 test (following an initial IGF-1 SDS < 0 or > 2.0 and clinically significant) has been eliminated.
5.3 Clinical Experience	Added paragraph about CT-102 trial	Documents bioequivalence of TransCon hGH delivered by two modalities: needle/syringe versus GH Auto-Injector
5.5 Summary of Risks and Benefits	Added language	To indicate comparable safety profile

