9.6.2. Stopping/Dose Reductions

The investigator or Medical Expert (and, if needed, with the ISC review) may stop or reduce the dose of investigational product for an individual subject at any time during the trial (please notify the Medical Expert as soon as possible). For example, consideration for stopping or reducing the dose may occur in the presence of the following symptoms and laboratory abnormalities:

- Severe hGH-related AEs at any time during the trial (eg, peripheral edema, severe headache, intracranial hypertension or other adverse drug reaction and/or abnormal laboratory values).
- Pregnancy: A subject must be discontinued from the trial if pregnant.
- IGF-1 > +2.0 SDS: The TransCon hGH dose may be decreased by approximately 20% to the next lower weight bracket, unless a different target SDS is identified in consultation with the Medical Expert. See Section 9.3 for details. (Although the prior *requirement* has been eliminated for a second [“confirmatory”] IGF-1 SDS test prior to dose titration, a second IGF-1 SDS test collected 5 days post-dose (± 1 day) remains optional at the investigator’s discretion.)

Any re-establishment of the prior dose due to a subsequent sub-optimal IGF-1 response should receive prior approval by the Medical Expert.

- In those subjects who have historically been dose titrated to a bracket different than expected for weight, the investigator may—at study visits—recommend maintenance of the current absolute dose until the visit’s IGF-1 SDS values are available. Once the IGF-1 SDS values are available, the investigator may then select the most appropriate dose volume or DCC presentation.
- Evidence of hypersensitivity to TransCon hGH
- Evidence of clinically significant pre-diabetes or diabetes (HbA1c > 6.2% and an absolute increase of 0.5% from the prior visit HbA1c): Confirmation of HbA1c level is required. Once confirmed, TransCon hGH dose may be decreased to the next lower weight bracket. If appropriate follow-up monitoring shows progressively worsening glucose intolerance, additional TransCon hGH dose adjustments may be appropriate.
- Clinical evidence of BIH based on history and physical exam, including visual changes, headaches, nausea, vomiting, and/or papilledema on funduscopy: TransCon hGH treatment should be discontinued while BIH is clinically managed.

Reinstitution of TransCon hGH treatment, preferably at a lower dose, should receive prior approval by the Medical Expert.

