14. STATISTICS

The Statistical Analysis Plan (SAP) will provide a detailed description of the planned statistical analyses. If discrepancies exist between the text of the statistical analysis as planned in the protocol and the final SAP, the final SAP will define the planned analysis of record.

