14.1. TRIAL ENDPOINTS

14.1.1. Safety Endpoints

The safety endpoints as measured throughout the long-term dosing of weekly TransCon hGH treatment include the following:

- Incidence of AEs
- Incidence of antibodies against hGH, including neutralizing antibodies
- Incidence of antibodies against PEG
- Incidence of antibodies against TransCon hGH
- Incidence of IGF-1 SDS > 2.0, > 3.0
- Parameters of HbA1c and lipids
- Hormone levels, including thyroid status and morning cortisol
- All other hematology and chemistry parameters
- Vital sign measurements

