8.7. OTHER ASSESSMENTS.....	22

9.	EFFICACY ANALYSES	22
9.1.	ANNUALIZED HV	22
9.2.	Δ HSDS	22
9.3.	IGF-1 SDS AND IGFBP-3 SDS	23
9.4.	SUBGROUP ANALYSIS.....	23
10.	PHARMACODYNAMICS ANALYSES	24
11.	PATIENT-REPORTED OUTCOMES.....	24
11.1.	PREFERENCE QUESTIONNAIRE.....	24
11.2.	CHILD SHEEHAN DISABILITY SCALE	24
11.3.	CONVENIENCE & OVERALL SATISFACTION DOMAINS OF THE TREATMENT SATISFACTION QUESTIONNAIRE FOR MEDICATION.....	25
11.4.	DEVICE USABILITY QUESTIONNAIRE.....	25
12.	REFERENCES.....	26

List of Abbreviations

ΔHSDS	change in height standard deviation score
μg	microgram
ADHD	attention-deficit/hyperactivity disorder
AE	adverse event
AGHD	adult growth hormone deficiency
C&OS-C	Convenience & Overall Satisfaction domains of the abbreviated 9-item Treatment Satisfaction Questionnaire for Medication - Child
C&OS-P	Convenience & Overall Satisfaction domains of the abbreviated 9- item Treatment Satisfaction Questionnaire for Medication - Parent
cm	centimeter
CSDS-C	Child Sheehan Disability Scale – Child
CSDS-P	Child Sheehan Disability Scale – Parent
eCRF	electronic case report form
FDA	Food and Drug Administration
GCP	Good Clinical Practice
GH	growth hormone
GHD	growth hormone deficiency
HbA1c	hemoglobin A1c
HV	height velocity
ICH	International Council on Harmonization
ICF	informed consent form
IEC	Independent Ethics Committee
IGF-1	insulin-like growth factor-1
IGFBP-3	insulin-like growth factor binding protein-3
kg	kilogram
MedDRA	Medical Dictionary for Regulatory Activities
mg	milligram
mL	milliliter
mPEG	methoxypolyethylene glycol
PD	pharmacodynamics
PQ-C	Preference Questionnaire – Child
PQ-P	Preference Questionnaire – Parent
SAE	serious adverse event
SAP	statistical analysis plan
SD	standard deviation
SDS	standard deviation score
TQSM	Treatment Satisfaction Questionnaire for Medication
TSQM-9	Abbreviated 9-item Treatment Satisfaction Questionnaire for Medication
WHO	World Health Organization

1. Overview

This Statistical Analysis Plan (SAP) describes and supplements the planned analysis and reporting for Ascendis Pharma Endocrinology Division A/S protocol TransCon hGH CT-301 EXT (enliGHten: A Multicenter, Phase 3, Long-term, Open-label Trial Investigating Safety and Efficacy of TransCon hGH Administered Once-Weekly in Children with Growth Hormone Deficiency (GHD) Who Have Completed a Prior TransCon hGH Clinical Trial), Protocol 1.0 dated 29 August 2017.

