11.4. Device Usability Questionnaire

The Device Usability Questionnaire will be administered during this trial to assess GH Auto-Injector comfort, ease-of-use, and safety from the point of view of the caregivers and subjects.

The questionnaire consists of eight statements that the subject or is asked to rank on a scale indicating level of agreement. The statements relate to the level of comfort, ease-of-use, and safety.

Descriptive analysis will be conducted for each question. Listing will also be provided.

12. References

- [1] Assay Development and Validation for Immunogenicity Testing of Therapeutic Protein Products (Draft Guidance), April 2016:
<https://www.fda.gov/downloads/Drugs/Guidances/UCM192750.pdf>
- [2] Shankar et al. (2014) Assessment and reporting of the clinical immunogenicity of therapeutic proteins and peptides-harmonized terminology and tactical recommendations, AAPS J. 2014 Jul;16(4):658-73

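### The SAP still requires confirmation in the high IGF-1 SDS safety endpoint after the protocol dropped it, and plans only by-visit percentages, with no count of children ever above the cut

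*SAP*

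**What the plan says.** SAP 3.3.1 gives the safety endpoint as "Incidence of IGF-1 SDS > 2.0, > 3.0 with confirmation", under a lead-in that places all safety endpoints over the whole of long-term dosing. Protocol 14.1.1 and the protocol synopsis give "Incidence of IGF-1 SDS > 2.0, > 3.0", with no confirmation. Protocol 9.6.1 and 9.6.2 say that a "second IGF-1 SDS test collected 5 days post-dose (± 1 day) remains optional", at the investigator's discretion.

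Two SAP sections produce tables with these cuts. SAP 8.3 plans the number and percent of subjects by visit above 2.0 and above 3.0, plus a listing of subjects with abnormally high values. SAP 9.3 repeats the cuts at each visit, by group and pooled. Neither applies a confirmation rule and neither counts across visits.

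The SAP says it was written to "Protocol 1.0 dated 29 August 2017". Protocol section 14 says that, where the two documents differ, "the final SAP will define the planned analysis of record".

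**The concern.** There are two separate problems.

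**Outdated definition.** The SAP names a confirmed endpoint, the protocol names an unconfirmed one, and the SAP's own tables follow the protocol. If the SAP wording governs, the endpoint depends on a repeat test done only when an investigator chooses to do it.

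**No subject-level incidence.** The primary objective is long-term safety, and +2.0 SDS is the top of the protocol's own IGF-1 goal (Protocol 9.6.1). After a value above it, Protocol 9.6.2 says "The TransCon hGH dose may be decreased by approximately 20% to the next lower weight bracket". A child high at one visit may therefore not be high at the next, while another child becomes high. By-visit percentages can stay low and flat while the number of children ever above the cut keeps growing, and no planned table would show it.

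**Working it through.** **Wording, side by side**

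- SAP 3.3.1: confirmed. Protocol 14.1.1 and synopsis: not confirmed. Protocol 9.6.1 and 9.6.2: second test optional. SAP 8.3 and 9.3: no confirmation rule.
- The deletion was deliberate. The protocol's summary of changes for US Amendment 1 records the confirmation words as removed "from Safety Endpoints on Incidence of IGF-1 SDS>2.0, 3.0", because the repeat test was no longer required.
- The reference to Protocol 1.0 explains the lag only in part. SAP 11.4 states "The Device Usability Questionnaire will be administered during this trial to assess GH Auto-Injector comfort, ease-of-use, and safety", and that questionnaire came in with the same US amendment. The SAP took up one change and not the other.

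**Do other planned outputs supply an ever-high count?**

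- SAP 9.3: its pooled column combines parent-study groups, not visits.
- SAP 5.3: one record per analysis window enters the summaries, the one closest to the target day. An optional repeat nearer the target can displace an earlier high value.
- Adverse event tables: Protocol 12.1.1 and 12.1.3 exclude out-of-range IGF-1 SDS unless a sign or symptom accompanies it.
- SAP section 10 (pharmacodynamics): listings only.
- SAP 8.3 listing: allows a hand count, but is not a summary.
- Contrast: SAP 8.2 plans antibody incidence as well as by-visit tables, and SAP 8.6 plans dose changes both by visit and overall.

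**How far the two quantities can differ**

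The documents give no rate of high values, so there is no plan figure to reproduce. Inputs:

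- K = 4 post-baseline visits to Week 52 (Weeks 13, 26, 39, 52) and K = 8 to Week 104, from SAP Table 2.
- About 300 subjects (Protocol section 8).
- By-visit prevalence p (2%, 5%, 10%), constant over visits: assumed.
- Within-child correlation ρ: assumed.

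*Bounds.* If the same children are high each time, the ever-high share is p. If different children are high each time, it is min(1, K·p). For K = 4:

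- p = 2%: 2% to 8%, or 6 to 24 of 300
- p = 5%: 5% to 20%, or 15 to 60 of 300
- p = 10%: 10% to 40%, or 30 to 120 of 300

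*Between the bounds.* With independent visits the share is 1 − (1 − p)^K; at p = 5% and K = 4, 1 − 0.95^4 = 18.5%. With an exchangeable latent-normal model, the share is 1 − E[(1 − q(U))^K], where U is standard normal, q(U) = P(Z > (z_p − √ρ·U)/√(1 − ρ)), and z_p is the upper p quantile of the normal distribution.

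| p | K | ρ = 0.3 | ρ = 0.5 | ρ = 0.7 |
|---|---|---|---|---|
| 2% | 4 | 7.1% | 6.4% | 5.3% |
| 5% | 4 | 16.4% | 14.4% | 12.0% |
| 10% | 4 | 29.5% | 25.9% | 21.7% |
| 2% | 8 | 12.5% | 10.4% | 7.9% |
| 5% | 8 | 26.7% | 21.9% | 16.8% |
| 10% | 8 | 44.4% | 36.7% | 28.8% |

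At p = 5% and ρ = 0.8, K = 4 gives 10.6%. Follow-up length alone moves the result: at p = 5% and ρ = 0.5 the share is 14.4% over four visits and 21.9% over eight, while the by-visit table shows 5% throughout.

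**The case against.** **The wording is editorial.** The operative tables already match the protocol, and other parts of the SAP show the same version lag. This stands: no count changes if 8.3 is followed. It also cannot be checked here whether the supplied SAP is the final version that governs. The endpoint and its tables still disagree within one document.

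**Incidence need not mean ever during the trial.** Neither document defines it that way, the lead-in also covers vital signs and chemistry, and by-visit proportions are defensible when follow-up is open-ended and unequal. That supports keeping the by-visit tables. It does not justify having nothing else for an endpoint named as an incidence, when the SAP plans more than by-visit figures for antibodies and dose changes.

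**Nothing is lost.** The listings keep all records, and the SAP allows further analyses labelled post hoc. True, but a named safety endpoint should not depend on a hand count or a post hoc table.

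**The size is assumed.** True. The 4p bound needs different children high at every visit, and the exchangeable model does not represent dose reduction after a high value. The bounds do not depend on that model, though they do assume the same p and the same children assessed at every visit.

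**An ever-high row is hard to interpret.** A child already above the cut at entry is counted like a new case, and unscheduled samples need not be taken at 5 ± 1 days post-dose. Both points stand as limits. The row shows ever-high, not new onset, and a footnote can isolate children who qualify only on unscheduled records but cannot make those records comparable.

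**Conclusion.** The concern holds on both parts. The confirmation wording is out of date against the current protocol and conflicts with the SAP's own tables; correcting it alters no count if SAP 8.3 is followed. The larger gap is that the endpoint has no planned subject-level summary, and the by-visit figures cannot supply one. At an assumed 5% per visit, the ever-high share at Week 52 could be anywhere from 5% to 20%. The prevalence, the correlation and constancy over visits are all assumptions, so these figures show how far the two quantities can part and do not forecast it. The trial is descriptive and no formal test is at risk, but this should be corrected before the final analysis because it concerns a named safety endpoint under a primary safety objective.

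**What to change.** 1. In SAP 3.3.1, delete the two words that require confirmation, so that the endpoint matches Protocol 14.1.1.
2. Keep the by-visit tables in SAP 8.3 and 9.3.
3. Add to SAP 8.3, by parent-study group and pooled, the number and percent of subjects with any IGF-1 SDS above 2.0 and above 3.0 after the extension baseline (the SAP 5.1 default for IGF-1), using scheduled and unscheduled records.
4. State the denominator: Full Analysis Set subjects with at least one post-baseline IGF-1 value. The default in SAP section 5 is all subjects in the cohort.
5. Because follow-up is open-ended and differs between children, give the rows twice. The first set runs through Day 408, the end of the Week 52 window in SAP Table 2 (x = 5: floor(91 × 4.5) − 1 = 408). The second covers the whole trial, with median and range of follow-up beside it.
6. Footnote the number who qualify only on an unscheduled record.

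The cost is two words deleted, a few rows and a footnote, all from data already collected. The drawback is that, for the same subjects, the ever-high percentage will be at least as high as any single-visit figure, and it depends on follow-up length and on how often a child is tested. The fixed-period rows and the footnote limit this but do not remove it.

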3.3.2. Efficacy Endpoints

The efficacy endpoints of long-term weekly TransCon hGH treatment include the following:

- Annualized HV
- Δ HSDS
- Proportion of subjects with IGF-1 SDS of 0 to +2.0. Additionally, cut points of -2.0 to +2.0 and -1.0 to +2.0 will be assessed.
- IGF-1 SDS
- IGFBP-3 SDS

3.3.3. Pharmacodynamic Endpoints

- Serum IGF-1 SDS at 5 days \pm 1day post-dose

3.3.4. Other Endpoints

- Preference for weekly TransCon hGH or daily Genotropin treatment
- Satisfaction with weekly TransCon hGH

4. Analysis and Reporting

4.1. Interim Analysis

This is an open label study. Interim analysis can be done at sponsor's discretion to support regulatory submission or product planning. An independent safety monitoring committee (ISC) will be established to monitor subject safety. Data used for ISC meetings will be handled according to the ICH E9 guidelines and therefore will not affect the study design and conduct from an efficacy perspective.

4.2. Final Analysis

All final, planned analyses identified in this SAP will be performed after the last subject has completed the last study visit and end of study assessments, and all relevant study data have been processed and integrated into the analysis database.

5. General Statistical Considerations

All analysis will be performed based on full analysis set and summaries will be presented overall and for subjects rolling over from Study CT-301 and Study CT-302 TransCon hGH group and Genotropin group separately. Descriptive summaries will be provided where appropriate for each of the primary and secondary variables.

Continuous, quantitative (absolute values at each time point and change from baseline if applicable) variable summaries will include the number of subjects (n) with non-missing values, mean, standard deviation (SD), standard error (SE), median, minimum, and maximum, unless otherwise specified.

Categorical, qualitative, variable summaries will include the frequency and percentage of subjects who are in the particular category. In general, the denominator for the percentage calculation will be based upon the total number of subjects in the study population for the cohorts, unless otherwise specified.

All data collected on eCRF will be presented in listings.

All analysis will be performed using SAS® Software version 9.4 or later.

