5.1. Baseline Data

Two baselines are defined. One is referred to as parent study baseline and the other one is extension study baseline.

Parent study baseline is defined as the last non-missing assessment collected before the first study treatment in the parent study. Extension study baseline is defined as the last non-missing assessment collected before the first study treatment in the extension study. Some of the information does not change and are only collected in parent studies, i.e., race, gender, and parent heights. In those cases, parent baseline data will be carried into extension study to serve as the baseline values.

For majority endpoints, including height, IGF-1 and etc., the extension study baseline values will be utilized for the analysis except for antibodies. For antibodies, the status before the first dose of TransCon will be considered as the baseline.

For annualized height, the rolling baseline will be used to calculate the annualized height velocity to make sure there is one-year gap in the calculation. In other words, from the 15-month (65 weeks) visit onwards, the baseline value used for each successive HV calculation was the patient's height at the visit 52 weeks previously, e.g. height at 13 week served as the baseline value to determine HV at the 65 week ('moving 52 weeks HV basis'). If height at visit 52 weeks previously is missing then most recent height prior to the visit will be used.

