5.2. Handling of Missing Data

In general, the observed data will be presented in listings. Imputed data will be used for summary analysis.

For determination of treatment-emergent adverse event (TEAE), if the start date and time of an AE are partially or completely missing, the AE will be assumed to be treatment-emergent if it cannot be definitely shown that the AE did not occur or worsen on or after the first dose in the study (worst case approach).

The following rules are used for TEAE determination where the AE has a missing start date.

If the start time of an AE is missing, but the start date is complete, an AE will only be excluded from treatment-emergent AEs if the start day is before day of first treatment or the start day is after end of study day.

If the start time and day are missing but the start month is complete, an AE will only be excluded from treatment emergent AEs if the start month is before month of first treatment or the start month is after end month of end of study month or if the stop date/time is before the start of first treatment.

If the start day and months are missing but the start year is complete, an AE will only be excluded from treatment-emergent AEs if the start year is before year of first treatment or if the start year is after end of study year or if the stop date/time is before the start of first treatment.

If the start date is completely missing, an AE will not be excluded from treatment emergent AEs unless the stop date/time is before the start of first treatment.

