5.5. Analysis Population

The Full Analysis Set includes all subjects who signed inform consent for this study and received at least one dose of study drug during the trial. The efficacy and safety analysis will be performed based on full analysis set.

6. Subject Disposition

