8.3. IGF-1 SDS

A descriptive table including the number and percentages of subjects by visit will be presented where:

- IGF-1 SDS > 2.0
- IGF-1 SDS > 3.0

Listings of IGF-1 and IGF-1 SDS for subjects with abnormally high IGF-1 SDS will be generated.

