9.3. IGF-1 SDS and IGFBP-3 SDS

A descriptive table including the frequency and percentages of subjects at each visit by each group and overall will be presented where:

- IGF-1 SDS < - 2.0
- $0 \leq \text{IGF-1 SDS} \leq 2.0$
- $-2.0 \leq \text{IGF-1 SDS} < 2.0$
- $-1.0 \leq \text{IGF-1 SDS} \leq 2.0$
- IGF-1 SDS > 2.0
- IGF-1 SDS > 3.0

The absolute values and change from baseline at each visit of the IGF-1, IGFBP-3, IGF-1 SDS and IGFBP-3 SDS will be presented with descriptive statistics. Listings will be generated for these outcomes.

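### The default percentage denominator in SAP section 5 is the cohort total, and the by-visit IGF-1 SDS tables name no other, so printed percentages fall with follow-up as well as with response

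*SAP*

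**What the plan says.** For categorical variables, SAP section 5 (General Statistical Considerations) sets a default: "In general, the denominator for the percentage calculation will be based upon the total number of subjects in the study population for the cohorts". The sentence closes with an escape clause: "for the cohorts, unless otherwise specified". For continuous variables the same section requires "the number of subjects (n) with non-missing values". It has no matching requirement for categorical ones.

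The population behind the total is the full analysis set, which "includes all subjects who signed inform consent for this study and received at least one dose of study drug during the trial" (SAP 5.5). Nothing in that definition depends on being in the study, or being measured, at a given visit.

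Two tables present IGF-1 SDS by visit:

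- SAP 8.3 (safety; above 2.0 and above 3.0): "A descriptive table including the number and percentages of subjects by visit will be presented where".
- SAP 9.3 (efficacy; six categories, including 0 to 2.0): "A descriptive table including the frequency and percentages of subjects at each visit by each group and overall will be presented where".

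Neither names a denominator. Nor does the Table 3 entry in SAP 5.4 for normalized IGF-1 SDS.

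On missing data, SAP 5.2 says "Imputed data will be used for summary analysis", but the rules that follow concern only adverse event start dates. SAP 5.1 does deal with a missing baseline: "Extension study baseline is defined as the last non-missing assessment collected before the first study treatment in the extension study". No comparable rule covers IGF-1 after baseline.

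**The concern.** A by-visit percentage is normally read as the share of subjects assessed at that visit who fall in the category. With the cohort total as denominator, a subject without a value stays in the denominator and counts as neither in range nor above 2.0 or 3.0. The percentage then mixes IGF-1 response with who is still being followed.

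In this trial n below N at later visits is built into the design. Visits continue every 13 weeks without a fixed end, and SAP Table 2 extends to a general Visit x. Participation ends with product availability, other access arrangements or epiphyseal closure, and may differ between countries (Protocol 10.1; SAP 3.1). Early leavers are not replaced (Protocol 8.3). SAP 4.1 allows interim analyses at the sponsor's discretion, and at such a cut some subjects may not yet have reached the later visits.

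The proportion in the 0 to +2.0 range is a secondary objective. The incidences above 2.0 and 3.0 are safety endpoints in a trial whose primary objective is long-term safety, and for these the dilution runs in the reassuring direction. The course over visits is also of direct interest, because Protocol 9.6.1 allows dosing to be adjusted with this range as the goal.

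**Working it through.** The documents give no IGF-1 proportion, no retention rate and no power calculation, so there is no planned figure to reproduce. The check is an identity followed by illustrations on stated assumptions.

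**Inputs**

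- N, the cohort total: up to about 300 (Protocol section 8) or about 400 (SAP 3.2). The percentages below depend only on n/N, so either gives the same result.
- n, the number with an IGF-1 SDS value in the visit window: not given. Write f = n/N. *Assumed:* f = 0.90, 0.75, 0.60.
- x, the number in the category: not given. *Assumed:* 60% of measured subjects in range and 10% above 2.0.

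**Step 1. Identity.**

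Printed percentage = x/N = (x/n) × (n/N) = (percentage among measured) × f.

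Relative understatement = 1 − f. It is zero when everyone is measured or when no one is in the category.

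**Step 2. Range.**

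| f = n/N | Relative understatement | 60% in range prints as | 10% above 2.0 prints as |
|---|---|---|---|
| 1.00 | 0% | 60.0% | 10.0% |
| 0.90 | 10% | 60 × 0.90 = 54.0% | 10 × 0.90 = 9.0% |
| 0.75 | 25% | 60 × 0.75 = 45.0% | 10 × 0.75 = 7.5% |
| 0.60 | 40% | 60 × 0.60 = 36.0% | 10 × 0.60 = 6.0% |

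**Step 3. Effect on a trend (constructed illustration).** If f goes from 0.90 to 0.60, the proportion among measured subjects must rise by a factor of 0.90/0.60 = 1.5 for the printed value to stay level. With N = 300, a rise above 2.0 from 27/270 = 10% to 27/180 = 15% prints as 27/300 = 9.0% both times. These values were chosen to show the mechanism; they are not a forecast.

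**Step 4. Could other SAP rules prevent this?**

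- *Visit windows (SAP 5.3).* The windows are contiguous, and unscheduled and early-termination visits are mapped to the nearest scheduled visit. Late or off-schedule samples can therefore fill a window. Nothing is carried forward to windows after a subject's last sample, so exit and visits not yet reached still reduce n.
- *Imputation (SAP 5.2).* If post-baseline IGF-1 were imputed for everyone, n would equal N and the dilution would vanish, but the result would rest on a rule the SAP does not give.
- *Table shells.* They could specify another denominator under the escape clause. They are not part of the SAP text.

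**Step 5. Can a reader recover n?** Yes. Three of the SAP 9.3 categories (below −2.0; −2.0 to below 2.0; above 2.0) cover the whole scale except a value of exactly 2.0, so their counts sum essentially to n. The continuous IGF-1 SDS summary must also show n.

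**The case against.** The strongest defence is that the sentence is only a default, hedged twice, and that shells may already use the right denominator. On that reading the SAP has an unclear denominator, not a demonstrated understatement. This stands as a condition on the conclusion. It does not remove the point, because the SAP states one rule, and a programmer who follows it will print x/N.

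Second, x/N is a correct percentage of the full analysis set, and n can be recovered from the same table. SAP 8.3 also lists subjects with abnormally high IGF-1 SDS, so no high value disappears. This stands and limits the consequence.

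Third, the sizes are assumed. The visit windows limit intermittent gaps, and Protocol 7.1.2 lists measures to keep data complete, so f may be close to 1 at early visits. This stands too.

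Fourth, x/n describes those who remain, who may be a selected group, so it is not a neutral true value. That is right, and it is the reason to print n beside N.

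Two stronger readings are tempting. A reader might infer that trends in IGF-1 will be hidden or reversed. The documents do not support that: they give neither retention nor IGF-1 proportions, and Step 3 shows only that it could happen. A reader might also infer that the preference questionnaire, completed only for former Genotropin subjects, will print badly diluted percentages. SAP 11.1 asks for no overall column; one would arise only through the general sentence in SAP section 5. Within the former-Genotropin column the parent form is affected only by missing questionnaires.

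**Conclusion.** The point holds as a conditional one. Followed as written, SAP section 5 makes each by-visit IGF-1 SDS percentage equal to the percentage among measured subjects times n/N. That understates both the in-range proportion and the incidences above 2.0 and 3.0 whenever n is below N and the category is not empty. The conclusion assumes that the shells do not override the default and that IGF-1 is not imputed.

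The relative understatement is 1 − n/N: 10%, 25% and 40% at assumed values of 0.90, 0.75 and 0.60. The actual size cannot be taken from the documents. It is likely to be small early and to grow at later visits.

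The analysis is descriptive, the counts are right, and n can be recovered. The fault is a misleading percentage for a secondary objective and two safety endpoints, not lost information. It should be corrected because the remedy is simple and brings categorical tables into line with what the SAP already requires for continuous ones.

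**What to change.** **SAP section 5.** Add wording to this effect:

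> For categorical tables by visit or timepoint (IGF-1 SDS categories, antibodies, pubertal status, questionnaires), the denominator is the number of subjects in the group with a non-missing or evaluable assessment at that visit or timepoint, shown as n beside the cohort N. For dose change by visit, it is the number of subjects on treatment with dosing records in that interval. Treatment-emergent adverse event, disposition and ever/never tables keep the cohort denominator.

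**SAP 5.2.** Add one sentence:

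> By-visit summaries of post-baseline IGF-1 SDS use observed values, with no imputation.

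A list of exceptions is better left out of 5.2. It would have to match date and derivation rules elsewhere in the SAP, such as the day-15 birth date in 5.4 and the statement in 7.3 that missing medication dates are not replaced.

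**Cost.** SAP wording and table shells only; no new data. If the shells already work this way, the change simply aligns the SAP with them. The downside is that later-visit percentages will describe a smaller and possibly selected group, which n beside N makes visible.
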